8.2 Inclusion Criteria

A subject must meet all the following inclusion criteria:

1. Aged 18 years or older.
2. Provided written informed consent.
3. Diagnosis of active scabies infestation confirmed by the presence of clinical signs and symptoms (evidence of burrows or typical inflammatory/noninflammatory lesions and pruritus) and either microscopic confirmation of scabies mite(s), ova or scybala by skin scraping or dermoscopy.
4. All female subjects of childbearing potential must agree to the use of a highly effective method of birth control until 16 weeks after administration of IP (Section 8.4.1).

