There will be no imputation for this endpoint. The denominator for the proportion will be subjects in each treatment group with a non-missing data point for this assessment, with subjects exposed to scabicides prior to their Day 28 assessment excluded from the analysis.

- **Plasma concentrations of moxidectin in a subset of index subjects selected for sparse PK sampling**

Approximately 20 subjects from each of the moxidectin cohorts (but not placebo) will be selected for sparse PK sampling. Moxidectin plasma concentrations will be determined at four time points, e.g., Day 0 (3- and 10-hours post-dose), Day 28, and Day 42. No pre-dose sample will be collected. Missing plasma concentrations will not be imputed.

- **The proportion of index subjects demonstrating all features of Complete Cure without regard to pruritus**

This endpoint is similar in definition as the primary efficacy Complete Cure endpoint except the pruritus component is not included in the definition, e.g.,:

- (1) Clinical cure (all signs and symptoms have completely resolved, including burrows and inflammatory/noninflammatory lesions).

and

- (2) Microscopic or dermatoscopic cure demonstrating the absence of mites, eggs, and/or scybala, and negative dermoscopy for burrows.

This will be derived from the individual assessments captured on the Day 28 Scabies Assessment eCRF page where:

- Lesion count is 0, and,
- Pruritus is ‘Present’ or ‘Absent’, and,
- Mites are ‘Absent’, and,
- Eggs are ‘Absent’, and,
- Scybala are ‘Absent’, and,
- Burrows (by dermoscopy) are ‘Absent’.

There will be no imputation for this endpoint except for subjects exposed to scabicides prior to their Day 28 assessment, who will be imputed as a non-responder (not cured). The denominator for the proportion will be subjects in each treatment group with a non-missing data point for this assessment.

- **The proportion of index subjects achieving clearance for each individual component of the Complete Cure endpoint**

This endpoint will examine each of the assessments captured on the Day 28 Scabies Assessment eCRF page individually. Subjects may be included in more than one component.

- Lesion count is 0, or,
- Pruritus is 'Absent', or,
- Mites are 'Absent', or,
- Eggs are 'Absent', or,
- Scybala are 'Absent', or,
- Burrows (by dermoscopy) are 'Absent'.

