There will be no imputation for this endpoint except for subjects exposed to scabicides prior to their Day 28 assessment, who will be imputed as a non-responder (not cured) for each individual component. The denominator for the proportion will be subjects in each treatment group with a non-missing data point for this assessment.

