9.8.2 Baseline Scabies Disease Characteristics

Descriptive statistics will be reported for the following scabies assessment characteristics at baseline (Day 0) for FAS subjects by randomized treatment group and overall:

- Number of lesions
- Scabies Severity:
 - Mild (≤ 10 lesions) (n, % FAS)
 - Moderate (11 to 49 lesions) (n, % FAS)
 - Severe (≥ 50 lesions) (n, % FAS)
- Diagnosed method
 - By microscopy (n, % FAS)
 - By dermoscopy (n, % FAS)

- Evidence of burrows (n, % FAS)
- Evidence of pruritus (n, % FAS)
- Evidence of nodules (n, % FAS)
- Evidence of mites (n, % FAS)
- Evidence of eggs (n, % FAS)
- Evidence of scybala (n, % FAS)
- Day 0 Method of assessment for mites, eggs, and scybala
 - Microscopy of skin scrapings (n, % FAS)
 - Dermoscopy (n, % FAS)
- Evidence of secondary bacterial infection (n, % FAS with secondary bacterial infection present)
- Number of body regions affected

Should the number of subjects randomized but not receiving study drug support aggregate tables by randomized treatment group, these tables may be repeated for this subgroup of subjects.

Additionally, the above scabies assessment characteristics will be repeated and stratified by region, summarized by randomized treatment group and overall.

Disease characteristics at Baseline and Day 28 will be listed.

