9.11.4.2 Adjustment for Baseline Lesion Count

An additional exploratory sensitivity analysis will assess the risk difference between each moxidectin dose group versus placebo after adjusting for Baseline lesion count. The analysis will use the same methodology for the primary analysis with appropriate imputations, but the logistic model will include randomized treatment group and Baseline lesion count. Region will be excluded from the model to keep the number of covariates small relative to the FAS sample size. Baseline lesion count will be categorized into three groups. The three baseline lesion groups are:

- Subjects with ≤ 10 lesions
- Subjects with 11 to 49 lesions
- Subjects with ≥ 50 lesions

In the model, dummy variables will be created for the lesion count categories using the subjects with ≤ 10 lesions category as the reference group. Each of the individual group proportion of FAS subjects achieving Day 28 Complete Cure and the three pairwise risk differences of each moxidectin group compared to placebo will be presented adjusting for Baseline lesion count. The 95% CIs will be displayed for each of the adjusted point estimates. The p-values for the risk differences will also be provided. This analysis will not be adjusted for multiplicity.

An additional sensitivity analysis will include the continuous metric for Baseline lesion count as a covariate after taking the natural log for each subject's Baseline count. The logistic model will then only include randomized treatment group and the logged Baseline lesion counts. The point estimates, CIs, and p-values described above will be presented adjusting for the continuous log transformed Baseline lesion count. Additional *ad hoc* analyses may be conducted to further explore the relationship between Baseline lesion count and Complete Cure.

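### SAP 6.3 counts a sign never recorded at Day 0 as cleared at Day 28, so component clearance can be inflated and differences between arms diluted

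*SAP*

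**What the plan says.** - **Eligibility.** Protocol 8.2, criterion 3, requires clinical signs ("evidence of burrows or typical inflammatory/noninflammatory lesions and pruritus") and "either microscopic confirmation of scabies mite(s), ova or scybala by skin scraping or dermoscopy". Both are lists of alternatives. Diagnosis is made at Screening, up to seven days before Day 0. The scabies assessment is done at Day 0 before randomization and again at Day 28 (Protocol 9.4.9 and Table 1).
- **Endpoint.** SAP 6.3 adds "The proportion of index subjects achieving clearance for each individual component of the Complete Cure endpoint". Only the later visit is used: "This endpoint will examine each of the assessments captured on the Day 28 Scabies Assessment eCRF page individually".
- **Denominator.** "The denominator for the proportion will be subjects in each treatment group with a non-missing data point for this assessment". Subjects exposed to scabicides before their Day 28 assessment are the exception, "who will be imputed as a non-responder (not cured) for each individual component".
- **Day 0 data.** SAP 9.8.2 tabulates burrows, pruritus, mites, eggs and scybala at Day 0 by arm (one entry begins "Evidence of eggs (n, % FAS"), and lists disease characteristics at both visits.
- **Status.** Exploratory endpoints are summarized descriptively (SAP 9.11.5). The list of cure rates in 9.11.5.1 does not include the component endpoint, and nothing else in 9.11.5 restricts its denominator.
- **Lesion counts.** A sensitivity model in SAP 9.11.4.2 will "include the continuous metric for Baseline lesion count as a covariate after taking the natural log". SAP 9.11.5.3 reports percent change from Baseline.

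**The concern.** Clearance implies that something was there to clear. Under criterion 3 a subject can enter with mites seen but no eggs or scybala, or with lesions but no burrows. SAP 9.8.2 treats each sign as something that may or may not be present at Day 0. The 6.3 definition ignores that status, so a subject without the sign at either visit counts as a success for it, unless the subject used a scabicide, in which case the same subject counts as a failure.

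At stake is how the component table is read in a dose-ranging study. For a sign seldom seen at entry, the rate may mostly reflect how often the sign was found at Day 0 and say little about what the dose did to it. The SAP already pairs Day 0 with Day 28 for lesion change, so using Baseline status would not be foreign to the plan.

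There is a related, conditional point. If a subject can enter on burrows alone and burrows are not in the lesion count, the Baseline count is 0. The logarithm and the percent change are then undefined, and the SAP gives no rule for that case.

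**Working it through.** **1. The plan's own figure.** The documents give no figure for component clearance. The only related figure is the power for the primary endpoint: about 75% with 50 per arm, 40% against 70%, two-tailed alpha 0.019 (SAP 4). With a pooled-variance Z-test and z = 2.3455:

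- pooled SE = √(2 × 0.55 × 0.45 / 50) = 0.0995; unpooled SE = √((0.24 + 0.21)/50) = 0.0949
- power = Φ((0.30 − 2.3455 × 0.0995)/0.0949) = 75.9%

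The figure reproduces, and nothing below changes it.

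**2. Formula.** For one component, let

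- b = share of subjects with it at Day 0, taken as equal across arms;
- c = share of those in whom it is gone at Day 28;
- q = share scored absent at Day 28 among those without it at Day 0.

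Then, with A for moxidectin and P for placebo:

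- reported rate = b·c + (1 − b)·q
- reported rate − c = (1 − b)(q − c), so an arm is inflated only if q > c
- reported difference = b(cA − cP) + (1 − b)(qA − qP), so the difference shrinks only if the gap in q is smaller than the gap in c

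**3. Signs do not newly appear (q = 100% in every arm).** The documents do not give b, c or q. Take cP = 40% and cA = 70%, borrowed from the primary endpoint purely as illustration.

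| b | Placebo | Moxidectin | Difference (points) |
|---|---|---|---|
| 1.00 | 40% | 70% | 30 |
| 0.90 | 46% | 73% | 27 |
| 0.75 | 55% | 77.5% | 22.5 |
| 0.50 | 70% | 85% | 15 |
| 0.25 | 85% | 92.5% | 7.5 |

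For example, at b = 0.50: 0.5 × 0.4 + 0.5 = 0.70 and 0.5 × 0.7 + 0.5 = 0.85. Between two doses at an assumed 60% and 80%, a 20-point gap becomes 15, 10 and 5 points at b = 0.75, 0.50 and 0.25. With the denominator limited to Day 0-positives, the rates are 40% and 70% whatever b is.

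**4. Signs do newly appear (b = 0.50, same c).**

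| qA | qP | Placebo | Moxidectin | Difference (points) |
|---|---|---|---|---|
| 95% | 80% | 60% | 82.5% | 22.5 |
| 95% | 65% | 52.5% | 82.5% | 30 |
| 95% | 50% | 45% | 82.5% | 37.5 |
| 90% | 40% | 40% | 80% | 40 |

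The difference can be diluted, unchanged or enlarged, and in the last row placebo is not inflated at all.

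**5. Scabicide rule alone.** Suppose 20% of placebo and 5% of moxidectin Day 0-negatives use a scabicide and no sign newly appears. Then qP = 80% and qA = 95%, and at b = 0.50 the difference is 22.5 points, where step 3 gives 15.

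**6. Precision with the restricted denominator.** At 50 per arm, 50b subjects remain: about 37, 25 and 12 per arm at b = 0.75, 0.50 and 0.25. The SE of the difference is √(0.45/(50b)) = 11.0, 13.4 and 19.0 points. For the all-subject rates of step 3 it is 9.2, 8.2 and 6.3 points.

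**The case against.** The strongest defence is that the definition matches its parent. SAP 6.1 defines Complete Cure by six findings at Day 28, whatever was seen at Day 0. An all-subject rate on the same six findings shows directly which one blocks Complete Cure. A subject with no eggs at Day 0 but eggs at Day 28 fails Complete Cure, and a Day 0-positive denominator would drop that subject from the egg rate. This stands. It is a reason to keep the all-subject rate, but not to call it clearance.

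A reader might infer that clearance is inflated in every arm, that differences between doses must shrink, or that placebo will show near-total clearance of rare signs. The documents do not support any of these. All three need Day 0-negative subjects to stay negative. Protocol 5.1 puts the usual burden at only 10 to 15 mites, and Protocol 5.4.3 says the sensitivity of scraping varies with the area chosen. A Day 0 absence may therefore be a missed finding in an infested subject, and an untreated subject may show the sign later. Scabicide users scored as not cleared also pull rates down. If Day 0 absence is mostly non-detection, q is close to c and restricting the denominator changes little.

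It is also true that SAP 9.8.2 shows Day 0 prevalence by arm. That helps a careful reader, but the table is not linked to this endpoint, and marginal prevalences do not give clearance among those with the sign.

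The zero-count point is open. Protocol 5.1 counts burrows among scabies lesions, whereas Protocol 9.4.9 handles burrows and the lesion count as separate steps. Even if zeros occur, the categorical lesion model keeps those subjects in its lowest group and absolute change can still be computed.

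**Conclusion.** The point holds in conditional form. SAP 6.3 scores as cleared a component that may never have been recorded, and no later section corrects this. If signs rarely newly appear, clearance is inflated and the absolute difference between arms is multiplied by roughly the Day 0 prevalence of the sign: on the assumed rates, 30 points become 22.5, 15 or 7.5 at prevalences of 75%, 50% or 25%. That assumption is plausible between active doses. It is less secure against placebo, where the difference could also be unchanged or larger. The actual size is unknown because the documents give no prevalence.

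The effect falls mainly on mites, eggs, scybala and burrows. It should be small for pruritus, which criterion 3 appears to require, and for lesion count unless subjects enter on burrows alone. The endpoint is exploratory, descriptive and untested. A reader should not carry the concern over to the primary endpoint, its power or its alpha. This is an inexpensive improvement in how a supporting table is defined and labelled.

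**What to change.** In SAP 6.3, before the Day 42 blind break:

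1. Keep the all-subject rate for each component, but rename it *absent at Day 28*, with a footnote that scabicide users are scored as not cleared.
2. Define clearance for each component among FAS subjects with that component present (or lesion count > 0) at the Day 0 assessment, and report n/N per arm.
3. Show separately, by arm, how many Day 0-negative subjects have the component newly present at Day 28.

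Conditional addition: state whether burrows are included in the lesion count. If a Baseline count of 0 can occur, use ln(count + 1) in 9.11.4.2 and compute percent change in 9.11.5.3 only where the Baseline count is > 0.

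The cost is SAP wording and some table programming. Day 0 status is already collected, and because it is recorded before randomization, the restricted denominator still compares randomized groups. The downside is small denominators for rarely seen signs: about 12 per arm at a prevalence of 25%, where the estimates would be imprecise. Under SAP 1.1 an analysis not defined in advance must be labelled post hoc, which is the reason to add this now.

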6.4 Safety Endpoints

- Incidence and severity of treatment emergent adverse events (TEAEs).
- Incidence of serious TEAEs.
- Incidence of TEAEs leading to study withdrawal and/or death.
- Incidence of TEAE attribution of relatedness to study drug.
- Changes from Baseline in 12-lead electrocardiograms (ECGs), laboratory assessments and vital signs.

Unless otherwise noted incidence refers to subject incidence.

7 DEFINITIONS

Terminology	Definitions
Age	Age will be calculated based on the month and year of birth entered in the Demography eCRF page, relative to the month and year of informed consent.
Baseline	The last non-missing assessment immediately prior to exposure to study drug
BMI	Body Mass Index, calculated as $\text{Weight (kg)} / (\text{Height (m)})^2$ (kg/m ²).
Clinical Cure	Demonstration that all signs and symptoms have completely resolved, including burrows, inflammatory/noninflammatory lesions and pruritus.
Complete Cure	Demonstration of both: (1) Clinical cure (all signs and symptoms have completely resolved, including burrows, inflammatory/noninflammatory lesions and pruritus). and

CONFIDENTIAL

Terminology	Definitions
	(2) Microscopic or dermatoscopic cure demonstrating the absence of mites, eggs, and/or scybala, and negative dermoscopy for burrows.
Complete Cure without regard to pruritus	Similar definition as Complete Cure except the pruritus component is not included in the definition, e.g., (1) Clinical cure (all signs and symptoms have completely resolved, including burrows and inflammatory/noninflammatory lesions). and (2) Microscopic or dermatoscopic cure demonstrating the absence of mites, eggs, and/or scybala, and negative dermoscopy for burrows.
Concomitant Medication	Medication taken on the day of or after the first study drug exposure. Concomitant medication may start prior to study drug administration if continued on the day of/after study drug administration.
Dispensing Error	The subject was dispensed less than or more than 16 capsules of moxidectin and/or placebo, but received the assigned treatment
Dosing Error	The subject was dispensed 16 capsules of moxidectin and/or placebo, but did not receive the assigned treatment
Dosing and Dispensing Error	The subject was dispensed less than or more than 16 capsules of moxidectin and/or placebo, and also did not receive the assigned treatment
Investigator Assessed Cure	Investigator selection of one of the three categories below that best describes the cure status of the subject at Day 28: 1. The scabies infestation is clear with all signs resolved, 2. The scabies infestation is clear with incomplete resolution of signs, and no additional treatment with standard of care is warranted, 3. The scabies infestation is not clear and additional treatment with standard of care is warranted.
Microscopic or Dermatoscopic Cure	Demonstration of the absence of mites, eggs, and/or scybala, and negative dermoscopy for burrows.
Randomized	A participant is considered randomized once the assignment of a Randomization Number for study MDGH-MOX-2002 is complete.
Scabicide	Scabicides are defined as any scabicide, including permethrin, ivermectin, benzyl benzoate, sulfur, lindane, crotamiton, malathion, tea tree oil, or spinosad used between Day 0 and Day 28. Scabicides do not include products used to manage the symptoms of scabies.
Screen Failure	Individuals who gave informed consent to screening but were not randomized.
Screened	Individuals who gave informed consent to screening.
Day 42 Completer	Subjects who completed the Day 42 visit in-clinic
Study Completer	Subject who completed the End of Study (Week 16) visit in-clinic.
Study Day	References to Study Day refer to the pre-specified visits defined in the protocol, where Day 0 is defined as the date subject was exposed to study drug. For randomized participants who do not receive study drug their Day 0 date will be their date of randomization. Study Day for events post Day 0 will be calculated as Event Date – Day 0 Date.

CONFIDENTIAL

Terminology	Definitions
	Study Day for events prior to Day 0 will be calculated as Day 0 Date – Event Date.
Study drug-related TEAE	Any TEAE which the investigator considered definitely, probably, or possibly related to study drug.
Study drug-unrelated TEAE	Any TEAE which the investigator considered unlikely to be or unrelated to study drug.
TEAE	Adverse event with an onset date on or after the date of study drug administration or an adverse event present before the administration of study drug that increases in severity.

8 ANALYSIS POPULATIONS

The analysis populations to be used for the efficacy and safety analyses are described below.

8.1 All Randomized Set

The All Randomized Set is defined as all subjects who were randomized irrespective of whether they received the study drug. Unless otherwise noted, the All Randomized Set will be the analysis set for subject disposition and protocol deviations.

A listing will be provided for All Randomized subjects to identify which analysis populations subjects are excluded from and the reason why.

8.2 Full Analysis Set

The Full Analysis Set (FAS) is defined as all randomized index subjects receiving study drug. Subjects in the FAS will be analyzed according to the treatment group to which they were randomized. The FAS will be the primary analysis set for the primary and, unless otherwise stated, all other efficacy analyses.

8.3 Safety Analysis Set

The Safety Analysis Set (SfAS) will include all index subjects exposed to study drug. Subjects will be analyzed according to the actual study drug received regardless of their randomized treatment group. Unless otherwise noted, the SfAS will be used for all safety analyses.

8.4 Per Protocol Analysis Set

The Per Protocol Analysis Set (PPAS) will include all index subjects exposed to study drug without any major protocol deviations that could confound the assessment and/or interpretation of the efficacy results. These protocol deviations will be identified by the study team prior to breaking the study blind for the Day 42 analysis. Subjects in the PPAS will be analyzed according to the actual treatment received regardless of their randomized dose group. Unless otherwise stated, the PPAS will be used for sensitivity analyses for the primary efficacy analysis.

8.5 Complete Analysis Set

The Complete Analysis Set will include all FAS subjects, except those FAS subjects exposed to scabicides prior to Day 28 and any FAS subject with a missing Day 28 Complete Cure assessment (including if any of the individual components of the Complete Cure endpoint is missing).

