Statistical significance will be based on a Dunnett adjusted two-tailed alpha level of 0.019 to account for the multiplicity of the three primary efficacy analyses and maintain a FWER of 0.05. For each comparison Wald type 95% confidence intervals incorporating Dunnett's critical value will also be calculated using the bootstrapped standard error (SE) for the adjusted risk difference as suggested by Steingrimsdottir *et al.* Should the bootstrap fail due to a small number of subjects in one of the two regions, the primary analysis will pool all subjects across regions (not adjust for region) and conduct the analysis using a Z-test for two independent proportions with pooled variance. Wald 95% confidence intervals with unpooled variance incorporating Dunnett's critical value will also be provided. These analyses will be conducted using the FAS.

As supportive analyses, the Day 28 Complete Cure rates for each moxidectin group and placebo as well as the RD and 95% CIs for each pairwise comparison, will be calculated within each region. Any significance tests of the risk difference conducted within region will be viewed as supportive and exploratory due to the potential lack of power.

The Day 28 Complete Cure status for subjects exposed to scabicides prior to their Day 28 assessment will be imputed as a non-responder (not cured) for the primary analyses using the FAS. Subjects missing Day 28 assessments due to events reasonably considered to be non-informative, i.e., SARS-CoV-2, will have their Day 28 Complete Cure rate imputed using multiple imputation (MI). Details of the imputation model and MI methods, as well as alternative approaches should the MI yield unreliable imputations due to overprediction or other issues, will be outlined in the SAP.

The estimand for each of the primary efficacy hypotheses outlined above is the comparison of the Day 28 Complete Cure rate of moxidectin without use of rescue medication versus the Day 28 Complete Cure rate of placebo without use of rescue medication. Rescue medication is defined as any scabicide, including permethrin, ivermectin, benzyl benzoate, sulfur, lindane, crotamiton, malathion, tea tree oil, or spinosad used between Day 0 and Day 28. Rescue medication does not include products used to manage the symptoms of scabies.

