As a sensitivity analysis the above primary efficacy analysis will be repeated using the PPAS as well as a completers analysis which will exclude any subject with a missing Day 28 Complete Cure assessment. Additional, sensitivity analyses will be conducted assessing the potential impact of missing data on the primary efficacy results and will be described in more detail within the SAP.

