1.2 Changes to Protocol Planned Analyses

The following changes have been made to the planned analyses described in the clinical study protocol MDGH-MOX-2002 Version 3 dated 28 Dec 2023:

- The description of the process for randomization, described under Section 10.1 of the current study protocol, was updated in this SAP Section 5.1. Instead of a unique screening number, a site specific sequential Subject Number was allocated to each subject who provided written informed consent. This Subject Number was used throughout the study to identify the subject. A unique Randomization Number was assigned to the subject upon randomization and this randomization number was only recorded on the Randomization electronic case report form (eCRF) page. Study drug was dispensed according to the Randomization Number, not according to the Subject Number.
- Two additional sensitivity analyses have been included to support the primary efficacy analysis:
 - A Completers Analysis excluding subjects with missing data for the primary endpoint with the exception of subjects exposed to scabicides.
 - An analysis that adjusts for Baseline lesion count as the sole covariate, other than randomized treatment group.
- The protocol states that sensitivity analyses will be conducted to assess the impact of missing data on the results. As such, a tipping point analysis has been included in the SAP.
- A repeat of the primary analysis within each Region will not be conducted due to anticipated small sample size within one of the Regions. However, descriptive analyses of the primary efficacy endpoint stratified by Region will be provided.

- Exploratory pairwise comparisons between each of the moxidectin dose groups have been added.
- For the non-informative missing data, the Complete Cure endpoint may be imputed via a fixed value using the methodology detailed in [Appendix 1](#). Should the missing data due to non-informative reasons be 5% of the total sample size, (approximately 200 subjects), a multiple imputation (MI) approach will be implemented using the methodology detailed in [Appendix 2](#).
- The following additional exploratory endpoints have been included in this SAP that are not otherwise listed in the current study protocol:
 - The Day 28 Complete Cure without regards to pruritus.
 - The proportion of index subjects achieving clearance for each individual component of the Complete Cure endpoint

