9.6 Protocol Deviations

A blinded review of protocol deviations documented during the study will be completed prior to the database freeze/lock and blind break for the Day 42 analysis. Protocol deviations are categorized at the time of entry into the Protocol Deviation eCRF page, but categorization will be reviewed during blinded review of all protocol deviations, and they will also be classified as major/minor:

- Consent procedures
- Inclusion/exclusion criteria
- Randomization procedures

- Concomitant medication/therapy
- Study procedures
- Serious adverse event (SAE) reporting
- Dosing
- Unblinding
- Scabies Assessment outside the Day 28 Visit Window
- Other Visit schedule/ interval
- COVID-19 related
- Other

Major protocol deviations will be defined as deviations that could potentially have a meaningful impact on the efficacy or safety results. Subjects with major protocol deviations that might impact efficacy will be excluded from the PPAS.

Some categories of major protocol deviations that might be considered as having a meaningful impact on the efficacy results include but are not limited to:

- Subjects failing any eligibility criteria,
- Subjects with treatment administration errors,
- Subjects randomized but not exposed to study drug (exclusion from FAS, PPAS, SfAS), and PK,
- Significant non-compliance with specified study visits windows,
- Administration of scabicides prior to the Day 28 visit (note: the exposure to scabicides prior to Day 28 is considered a major protocol deviation and subjects will be considered non-responders for the primary analysis)

Protocol deviations leading to missing data will also be reviewed to assess the reasons why the data are missing and whether they are considered informative or non-informative reasons for the purposes of handling of missing data described in Section 9.11.2. Where the reason(s) for missing data is unknown and/or not fully documented, the default will be to assume informative missing. Examples of non-informative missing data might be:

- Missed visit due to weather, travel, or childcare,
- Missed visit due to COVID-19 or COVID-19 exposure,
- Missed assessment due to equipment failure.

All determinations of informative and non-informative missing data will be fully documented and reported.

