9.11.3 Sensitivity Analyses for Primary Analysis of Day 28 Complete Cure

9.11.3.1 PPAS and Complete Data Analyses

Sensitivity analyses for the above primary efficacy analysis will be conducted using the same methodology outlined above for the primary efficacy analysis. The first sensitivity analysis will repeat the primary efficacy analysis using the PPAS. The second sensitivity analysis will repeat the primary efficacy analysis for the Complete Analysis Set.

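### SAP 8.5 drops scabicide-exposed subjects from the completers sensitivity analysis, against SAP 1.2 and protocol 15.6.2, so that analysis no longer tests the primary estimand

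*SAP*

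**What the plan says.** The plan describes the completers analysis in three places, and they do not agree.

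- Protocol 15.6.2 plans a "completers analysis which will exclude any subject with a missing Day 28 Complete Cure assessment". Scabicide exposure is not a ground for exclusion.
- SAP 1.2 lists, among the changes from the protocol, "A Completers Analysis excluding subjects with missing data for the primary endpoint with the exception of subjects exposed to scabicides". On its natural reading, scabicide-exposed subjects stay in.
- SAP 8.5 defines the set to be used: "The Complete Analysis Set will include all FAS subjects, except those FAS subjects exposed to scabicides prior to Day 28". Subjects with a missing Complete Cure are then excluded as a second, separate ground.

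SAP 9.11.3.1 ties the analysis to the third definition: "The second sensitivity analysis will repeat the primary efficacy analysis for the Complete Analysis Set".

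For the primary analysis the plan is consistent. Protocol 15.6.2 says: "The Day 28 Complete Cure status for subjects exposed to scabicides prior to their Day 28 assessment will be imputed as a non-responder". The estimand table in SAP 3.4, the endpoint definition in SAP 6.1 and the missing-data rules in SAP 9.11.2 say the same. SAP Appendix 2 keeps these subjects in the multiple-imputation dataset as not cured, whether or not Day 28 was observed.

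**The concern.** A programmer cannot satisfy both SAP 1.2 and SAP 8.5. SAP 1.1 gives the SAP precedence over the protocol, but that does not settle a conflict within the SAP. SAP 1.2 also does not list removal of scabicide users as a change from the protocol.

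The choice matters because scabicide use happens after randomisation and the estimand counts it as failure. Protocol 11.2.3 and 14.2 keep these subjects on study, so most should have a Day 28 assessment and would not be missing at all. Removing them changes the question to cure among those who were not rescued. If the result then differs from the primary one, the reader cannot tell whether missing data or the deleted failures caused it. With two prespecified definitions left standing, the choice between them could also be made after the results are known.

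**Working it through.** **1. Who is kept under each text**

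| Subject | Primary analysis | Protocol 15.6.2 completers | SAP 1.2 completers | SAP 8.5 set |
|---|---|---|---|---|
| Scabicide used, Day 28 observed | Not cured | Kept | Kept | Removed |
| Scabicide used, Day 28 missing | Not cured | Removed, read literally | Kept, not cured | Removed |
| No scabicide, Day 28 missing | Imputed | Removed | Removed | Removed |

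SAP 8.5 stands alone on the first row. SAP 6.3 is a useful comparison: its cure endpoints do not impute ordinary missing data, yet still count scabicide users as not cured.

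**2. The plan's own power figure**

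Inputs from SAP 4: n = 50 per arm, 40% vs 70%, two-tailed alpha 0.019 (z = 2.3455), Z-test with pooled variance.

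- Null SE = sqrt(0.55 × 0.45 × 2/50) = 0.0995
- Alternative SE = sqrt(0.24/50 + 0.21/50) = 0.0949
- Power = Φ((0.30 − 2.3455 × 0.0995)/0.0949) = 75.9%

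The plan says approximately 75%, so the figure reproduces. The 40% placebo rate is already a rate with scabicide users counted as failures (protocol 5.4.2). It is therefore the right starting point.

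**3. Effect of deletion**

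If a fraction s of an arm used scabicides, all are failures in the primary analysis. Deleting them leaves the number cured unchanged and reduces the denominator from n to n(1 − s). The cure rate becomes p/(1 − s), which is higher in every arm that has users.

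**4. Size**

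The documents give no scabicide rates, so the rates below are assumptions. Starting point: 20/50 vs 35/50 cured, with no other missing data. Power uses the same pooled-variance test throughout.

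| Use, placebo / moxidectin | Placebo | Moxidectin | RD (points) | Power |
|---|---|---|---|---|
| Users kept as failures | 20/50 = 40.0% | 35/50 = 70.0% | 30.0 | 76% |
| 10% / 2% | 20/45 = 44.4% | 35/49 = 71.4% | 27.0 | 62% |
| 20% / 6% | 20/40 = 50.0% | 35/47 = 74.5% | 24.5 | 51% |
| 30% / 8% | 20/35 = 57.1% | 35/46 = 76.1% | 18.9 | 30% |
| 20% / 20% | 20/40 = 50.0% | 35/40 = 87.5% | 37.5 | 92% |

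With unpooled variance throughout, the 20%/6% case goes from 79.3% to 52.6%. The two methods should not be mixed.

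**5. Where the direction turns**

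The difference stays at 30 points when 0.70/(1 − s1) − 0.40/(1 − s0) = 0.30, where s0 is placebo use and s1 moxidectin use. With s0 = 20% this gives 0.70/(1 − s1) = 0.80, so s1 = 12.5%. With s0 = 10% it gives s1 of about 6%. Below those values the difference shrinks; above them it grows.

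With no true difference (40% in both arms), 10 placebo and 2 moxidectin users give 20/48 − 20/40 = −8.3 points. The reverse split gives +8.3.

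**The case against.** Four points can be made for the plan.

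**Direction.** A reader might infer that the set always works against moxidectin, because rescue should be commoner on placebo. The documents do not support that. They give no rates, and step 5 shows that the sign depends on the split. Exposure also need not mean failure: protocol 11.2.3 counts ivermectin taken for any indication. The bias is real, but its sign is unknown.

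**The PPAS.** It probably loses the same subjects, since SAP 9.6 lists "Administration of scabicides prior to the Day 28 visit" among major deviations that might affect efficacy. A reader might call that a second error. It is not: protocol 11.2.3 and 15.3.2 and SAP 8.4 and 9.6 agree with one another, and dropping users of prohibited medication is ordinary for a per-protocol set. It does mean that the completers analysis is the one of the two in SAP 9.11.3.1 where keeping these subjects matters.

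**Missing data.** A reader might infer that the missing-data assumption goes untested. It does not: the tipping-point analysis in SAP 9.11.3.2 probes imputed outcomes separately, and SAP 1.2 presents it as meeting the protocol's commitment.

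**The protocol's wording.** Protocol 15.6.8 refers to status missing for reasons other than scabicide exposure, which could be read as treating exposure as a kind of missingness. That softens the conflict with the protocol. It does not touch the conflict between SAP 1.2 and SAP 8.5, and protocol 15.6.2 turns on a missing assessment, not on exposure.

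The contradiction inside the SAP survives all four.

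**Conclusion.** The concern holds for one sensitivity analysis. SAP 8.5 contradicts SAP 1.2 and protocol 15.6.2, and following it deletes subjects whom the estimand counts as non-responders. Under the assumed scabicide rates the 30-point difference moves to anywhere between 18.9 and 37.5 points. These figures rest on the planning cure rates, on an unadjusted comparison without the region term, and on there being no other missing data.

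A reader might go further and doubt the primary result. Nothing supports that: the primary analysis, the estimand and the multiple-imputation dataset all keep scabicide users as not cured. Nor does any success rule depend on this sensitivity analysis, so the power figures show how far its result could drift and are not a loss of trial power. The point should be fixed, but it does not put the trial's main conclusion at risk.

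**What to change.** Before the Day 42 unblinding, amend SAP 8.5 so that a FAS subject is excluded only if Day 28 Complete Cure is missing for a reason other than scabicide exposure. Scabicide-exposed subjects stay in as non-responders, as SAP 1.2 states.

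If an analysis without scabicide users is also wanted, give it its own named set, list it in SAP 1.2 as a change from the protocol, and state that its estimand differs from the primary one.

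Leave the PPAS definition as it is.

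The cost is SAP wording and the matching population flag in the programs. It needs no new data and no change to the primary analysis. SAP 1.1 already provides for documented amendments before unblinding.
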